8.2.4 Sample Processing Directions

Upon receipt of CPT tubes upright in rack at RT:

1. Within two hours of blood draw, begin isolation of PBMC utilizing CPT to PBMC protocol—**be sure to re-mix CPT tube by inverting 8 times before centrifugation.**
2. Count cells record number of PBMC's on requisition.
3. Proceed according to the following algorithm:
 - a. 2×10^6 cells for pellet in PBS for DNA extraction.
 - b. 1×10^6 cells for telomerase extraction in CHAPS buffer.
4. Freeze PBMC for DNA pellet(s) at -80°C to store for future extraction.
5. Perform telomerase extraction on fresh cells per IBC protocol.

9 ASSESSMENT OF SAFETY

9.1 Specification of Safety Parameters

Safety assessments will include recording of AEs, which will be followed until the event has resolved or the condition has been deemed stable by the Investigator. At each visit, the Investigator will evaluate the subject to determine whether any AE has occurred. AEs may be directly observed, spontaneously reported by the subject, or obtained by questioning the subject at each study visit. Subjects should be questioned in a general way without asking about the occurrence of specific symptoms; at each visit, they will be asked standard questions to elicit any medically related changes in their well-being.

All SAEs will be reported to regulatory authorities and the site IRB within required time frames.

9.1.1 Adverse Events

The Investigator is responsible for reporting all AEs observed or reported during the study, regardless of clinical significance or potential causal relationship to study medication.

An AE is any untoward medical occurrence in a human subject administered the study device, temporally associated with the subject's participation in the research, whether or not considered related to the subject's participation in the research. Subjects will be instructed to contact the Investigator at any time after randomization if any symptoms develop.

9.1.2 Serious Adverse Events

An SAE is defined as any event that results in death, is immediately life-threatening, requires inpatient hospitalization or prolongation of existing hospitalization, results in persistent or significant disability/incapacity or is a congenital anomaly/birth defect.

Important medical events that may not result in death, be life-threatening, or require hospitalization may be considered SAEs when, based on appropriate medical judgment, they may jeopardize the subject and require medical or surgical intervention to prevent one of the outcomes listed in this definition.

9.2 Time Period and Frequency for Event Assessment and Follow-Up

All AEs reported by subjects or observed during the study will be recorded. All AEs shall be recorded in subject's file regardless of perceived causality. AEs will be assessed from the first device treatment (screening visit) to the last device treatment. AE form will be collected during each study visit at OCNS.

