2.3.1 Potential Risks

The most common side effects of the device are dizziness, headache, and local skin irritation. Dizziness and headache most commonly occur at higher current levels but will be minimized by having the first electrical stimulation session performed at the research center to make sure the study protocol is tolerated. Subjects who cannot tolerate the study protocol will be dropped from the study. Phlebotomy has a low risk of bruising, swelling or pain at the site, and a very low risk of infection.

The collection of data contains the inherent risk of loss of privacy. This risk will be minimized by adequate training of all study staff according to institutional guidelines, use of unique subject identifiers, and by keeping data in password protected computer databases and/or locked cabinets. An informed consent document was approved by the local Institutional Review Boards at UCLA and a recruitment waiver was obtained from the IRB at the Greater Los Angeles VA. All subjects will read and document understanding of the consent form prior to enrolling in the study.

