5.6 Subject Withdrawal

Study participation is voluntary and subjects have the right to withdraw from the study at any time. The investigator may terminate a subject's participation if necessary.

5.6.1 *Reasons for Withdrawal*

Subjects are free to withdraw from participation in the study at any time upon request.

An investigator may terminate a study subject's participation in the study if:

- Any clinical AE or SAE, laboratory abnormality, or other medical condition or situation occurs such that continued participation in the study would not be in the best interest of the subject.
- The subject meets an exclusion criterion (either newly developed or not previously recognized) that precludes further study participation.
- Non-compliance with study protocol

5.6.2 *Handling of Subject Withdrawals or Subject Discontinuation of Study Intervention*

An adverse events report will be collected from subjects who choose to withdraw from the study. Subjects will be required to return study device to research personnel.

In the event of an (S)AE, every effort will be made to obtain follow-up data on any subject who discontinued device treatment due to an (S)AE. To the extent possible, any withdrawn subject will be followed until the (S)AE has resolved.

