7.4 Final Study Visit (Visit 3)

This visit will occur at the Oppenheimer Family Center for Neurobiology of Stress. This visit will take approximately 2 hours and will occur after 8 weeks of

treatment, Week 8 + 1 week. Subjects will be asked to bring the CES device to return. The study coordinator will collect the tracking diary for weeks 5-8. The subjects must complete the final set of questionnaires:

- Mini International Neuropsychiatric Interview (MINI)
- Hospital Anxiety and Depression Scale (HADS)
- Mental Health Continuum Short Form (MHC-SF)
- Patient Reported Outcomes Measurement Information System (PROMIS-29)
- Positive and Negative Affect Schedule Short Form (PANAS-SF)
- Connor-Davidson Resilience Scale (CD-RISC)
- Perceived Stress Scale (PSS)
- Patient Health Questionnaire (PHQ)
- Columbia-Suicide Severity Rating Scale (C-SSRS) Self Report Screener - Since Last Contact
- Impression of Global Improvement Scale

The subjects will have vital signs and weight measured and have the final blood draw performed by a nurse. Adverse events and concomitant medication report will be collected as well.

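### Section 9.2 closes AE assessment at the last device treatment, contrary to 9.1 and 7.4, and Section 5.6.2 states no exit AE report for subjects whom the investigator removes

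*Combined protocol and SAP*

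**What the plan says.** Section 9.2 holds three rules that do not share an end point. The recording rule is broad: "All AEs reported by subjects or observed during the study will be recorded". The window is narrow: "AEs will be assessed from the first device treatment (screening visit) to the last device treatment". The collection rule goes by visit: "AE form will be collected during each study visit at OCNS". Section 9.1 also goes by visit: "At each visit, the Investigator will evaluate the subject to determine whether any AE has occurred".

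Visit 3 (Section 7.4) follows 8 weeks of treatment, with a window of Week 8 plus 1 week. There, "The subjects will have vital signs and weight measured and have the final blood draw performed by a nurse", and the next sentence of 7.4 has adverse events collected at the same visit. Section 8.2.1 gives only two draws, at Visits 1 and 3. Under Section 7.2 the first draw comes after the first device session.

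Section 9.1.1 ties an AE to participation in the research, whether or not it is thought to be related, and adds an instruction with no end date: "Subjects will be instructed to contact the Investigator at any time after randomization if any symptoms develop".

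For early exits, Section 5.6.2 says: "An adverse events report will be collected from subjects who choose to withdraw from the study". It also requires the device to be returned, asks for follow-up data on anyone who stopped the device because of an (S)AE, and has withdrawn subjects followed, as far as possible, until the (S)AE resolves. Section 5.3 opens the final visit only to subjects who used the device on at least 5 of 7 days per week. Section 6.3 provides daily calls in week 1 and weekly calls in weeks 2 to 8, with AEs noted.

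**The concern.** There are two defects.

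First, read literally, the window sentence in 9.2 shuts before Visit 3, where the protocol collects AEs and draws blood for the second time. Section 2.3.1 lists that procedure among the study risks: "Phlebotomy has a low risk of bruising, swelling or pain at the site, and a very low risk of infection". Staff following the window sentence could leave out an event dated after the last session, while staff following the visit rule would record it. The window also closes early for anyone who stops using the device but stays in the study.

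Second, the exit report depends on who ended participation. The protocol has several routes by which the investigator ends it, and none of them is a choice by the subject. A subject who uses the device less because of side effects could fall below the compliance minimum, lose the final visit and have no stated exit report. What is at stake is the completeness of the AE record for subjects in whom side effects may have shaped adherence or exit.

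**Working it through.** The documents state no figure to reproduce. The check sets the rules side by side and adds simple date and count arithmetic.

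**1. Where AE assessment ends**

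- Window sentence in 9.2: last device treatment.
- Form rule in 9.2 and evaluation rule in 9.1: every visit, so Visit 3 is included.
- AE collection in 7.4: Visit 3.
- Subject-initiated contact in 9.1.1: no stated end.

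Visit 3 lies between the end of week 8 and the end of week 9. The gap after the planned last session is therefore 0 to (9 − 8) × 7 = 7 days, or about 7 at most. It is outside the window sentence but inside the reach of the Visit 3 AE report. The draw at Visit 3 (1 of 2 draws, 8 of 16 mL) also falls after the window sentence closes. After Visit 3 no contact is scheduled, because the calls in 6.3 cover weeks 1 to 8 only.

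**2. Who has a stated exit AE report**

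- Leaves by choice (5.6.2): yes.
- Non-compliance (4.1, 5.6.1): none stated. If use is below 5 of 7 days, the final visit is closed as well (5.3).
- Opiate use (6.4): none stated. Medication changes are picked up on the weekly call, which notes AEs.
- Newly met exclusion criterion (5.6.1): none stated.
- Increased suicidal thoughts (5.4): none stated. The since-last-contact screener is given at Visits 2 and 3, where AEs are collected, and follow-up is settled before discharge.
- Intolerance (2.3.1, 7.2): none stated. The first session takes place at the center, at a visit covered by the AE form rule.
- AE or SAE (5.6.1): no exit report stated, but 5.6.2 follows the known event. It does not ask about new ones.

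**3. What covers a removed subject before removal**

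Calls are daily in week 1 and weekly afterwards. If they are made on schedule, the stretch not yet asked about at removal is at most about 7 days from week 2 onwards. The diary also records side effects. It is collected at Visits 2 and 3 (7.3, 7.4), and 5.6.2 mentions return of the device but not of the diary.

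**4. How many exits**

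- From the plan's counts: 55 − 2 × 22 = 55 − 44 = 11.
- From the stated attrition: 0.25 × 55 = 13.75, about 14.

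So 11 to 14 early exits are implied. The documents give no split between voluntary and investigator-ended exits. The number without a stated exit report could lie anywhere from 0 to all of them.

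**The case against.** The strongest reply is that one sentence of 9.2 should not be read alone. The same section records every AE reported or observed during the study and takes a form at each visit, and 9.1 and 7.4 agree. Events in the gap can be reported at Visit 3, and events during the visit can be seen and recorded there. Removed subjects were reached by calls, diary and visits until they left, and a subject who stopped because of an (S)AE has explicit follow-up. All of this stands. It makes the first defect a contradiction to be reconciled rather than missing collection. It does not supply an exit report for investigator-ended cases.

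A reader might go further in four ways that the documents do not support:

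- That the final draw, the gap and all removed subjects fall outside AE capture. The provisions just listed contradict this.
- That phlebotomy risk goes unmonitored for half of the draws. The second draw is done by a nurse at a visit that collects AEs. Only delayed events lack a scheduled contact, and 9.1.1 invites subjects to report them.
- That most of the course is lost for someone who stops early. Stopping at day 10 of 56 gives (56 − 10)/56 = 82% outside the literal window. That is a hypothetical case under the narrowest reading; if still enrolled, the subject is due weekly calls and the Visit 2 form.
- That a between-arm safety comparison is biased toward no difference. Section 10 plans no such comparison, and the direction would hold only if side effects of the active device drove non-adherence.

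**Conclusion.** The point holds as two wording defects with a modest effect. The end of the AE window in 9.2 contradicts 9.1, 7.4 and the form rule in 9.2 itself, over a gap of 0 to about 7 days plus the Visit 3 procedures. Section 5.6.2 leaves investigator-ended exits with no stated AE report, and 5.3 also closes the final visit to those with low compliance. Followed as written, the rules make ascertainment at exit depend on adherence and on who ended participation.

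The size cannot be fixed. The 11 to 14 exits are planning figures, their split is not given, and the readable results text gives completers only (11 sham, 13 active in Section 13.2). That adherence or removal is related to side effects is an assumption; the documents neither show it nor rule it out. The limit of about 7 days since the last call assumes that the calls in 6.3 were made on schedule.

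**What to change.** Reconcile 9.2 with 9.1 and 7.4: state that AEs are assessed from the first device treatment through Visit 3 or the exit contact, regardless of device use. In 5.6.2, require an AE report from all subjects who withdraw or are withdrawn, for any reason, taken at the device return that the section already demands. A call after Visit 3 for delayed phlebotomy events is optional, given the standing instruction in 9.1.1.

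The cost is two sentences and a few more minor events to record. Because the document already carries results (Section 13), new wording cannot recover reports that were not taken. What can still be done for this trial is disclosure: any safety report should state which AE window was applied and how many investigator-ended exits had no AE report.

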9.3 Characteristics of an Adverse Event

9.3.1 Relationship to Study Intervention

The Investigator is obligated to estimate the relationship between the device and the occurrence of each AE or SAE by using his or her best clinical judgment. Other elements, such as the history of the underlying disease, concomitant therapy, other risk factors, and the temporal relationship of the event to the investigational product, will be considered and investigated.

To assess relationship of an event to study intervention, the following guidelines are presented in Table 1.

Table 1 Assessment of Causality/Relatedness of AEs and SAEs

Categories	Definition
Definitely related	This relationship suggests that a definite causal relationship exists between the device treatment and the AE, and other conditions (concurrent illness, progression/expression of disease state, or concurrent medication reaction) do not appear to explain the event.
Probably related	This relationship suggests that a reasonable temporal sequence of the event with device treatment exists and, based upon the known side effects of device treatment, known or previously reported adverse reactions to device treatment, or judgment based on the Investigator's clinical experience, the association of the event with the study device seems likely.
Possibly related	This relationship suggests that device treatment may have caused or contributed to the AE (i.e., the event follows a reasonable temporal sequence from the time of device treatment and/or follows a known response pattern to the study treatment but could also have been produced by other factors).
Not related	This relationship suggests that there is no association between the study device and the reported event.

9.3.2 **Expectedness of SAEs**

The Study PI will be responsible for determining whether an SAE is expected or unexpected. An adverse event will be considered unexpected if the nature, severity, or frequency of the event is not consistent with the risk information previously described for the intervention.

9.3.3 **Severity of Event**

The Investigator will make an assessment of severity for each AE and SAE reported during the study. The assessment will be based on the Investigator's clinical judgment. The severity of each AE should be assigned to one of the categories shown in Table 2.

Table 2 Common Adverse Event Grading Scale

Grade	Definition
Mild	Aware of sign or symptom, but easily tolerated
Moderate	Discomfort enough to cause interference with usual activities
Severe	Incapacitating, with inability to work or perform usual activities

An AE that is assessed as severe should not be confused with a SAE. Severity is a category used for rating the intensity of an event (such as mild, moderate, or severe), and both AE(s) and SAE(s) can be assessed as mild, moderate, or severe. An event is defined as serious when it meets one of the predefined outcomes described in 9.1.2.

9.4 **Reporting Procedures**

AE's that meet the criteria for reporting per the UCLA IRB guidelines are reported to the IRB within 10 working days of awareness where the UCLA IRB is the responsible IRB, and is determined by the UCLA PI to be either:

- Unexpected, and related or possibly related to the research activity, and serious (i.e. placing subjects at greater risk of harm than previously known) or
- Expected and related to but indicating a higher severity or frequency of occurrence (i.e. a trend) than was known or described in the current approved ICF and therefore a new identified risk.

SAEs or deaths that are unanticipated, serious, and possibly related to the study intervention will be reported to the UCLA IRB in accordance with their requirements which is within 3 working days of awareness.

10 STATISTICAL ANALYSIS PLAN

10.1 Sample Size

G*Power 3.1 was employed to calculate the number of subjects needed per group to detect a large group differences, slightly less than a 1 standard deviation difference (Cohen's effect, size, $d=.80$) in the effect of daily CES treatment on emotional well-being and PBMC telomerase activity. Based on a one tailed superiority test of improvement (active > sham CES treatment) and an alpha = .05, 22 subjects per group are required to provide adequate statistical power (80%) for the analysis (Noncentrality parameter=2.59, Critical $t(40)=1.68$. To meet this criteria we will include 22 completed subjects per group.

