4.2 Study Population

Approximately 55 male subjects will be screened in an effort to obtain 22 subjects in each treatment group after randomization. Due to the difficulty with recruitment of eligible Veterans in this feasibility pilot, the study period was extended and non-Veterans meeting the other inclusion criteria were recruited. The study enrollment was limited to 24 completed subjects based on insufficient resources to complete the study beyond the extended recruitment period.

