12.3 Study Records Retention

Upon completion of the study, the coding key and all identifiers will be destroyed, rendering the data anonymous.

With subject permission, we may store specimen data with or without subject's name or identifying information for future use. Retention of blood specimens after the end of the study for use in future research must be granted permission from the subject on the ICF. Subjects will give permission on the ICF if they agree to keep their name and other identifying information with their specimens. See 11.4 for future use of stored specimens plan.

13 RESULTS:

13.1 Feasibility: This was a feasibility study, initially powered for a sample size of 44. We fell far below the recruitment goals, despite 2 years of recruitment, finding a lack of interest for this intervention from the desired patient population. Therefore we consider the feasibility goal to have been a failure. The results should be interpreted with caution as the study was likely underpowered and the real world acceptability of the intervention in the context of this study was not desirable enough to recruit participants.

[figure not shown]
13.2 Baseline values and demographics:

11 subjects completed the Sham treatment and 13 completed the active treatment. No baseline differences in age, body mass index, HAD anxiety, HAD depression, or telomere length were identified between subjects randomized to the sham or active device groups. Both groups had 5 Veterans. Two subjects did not have baseline BMI measured. 1 subject did not have sufficient sample to complete the Telomere length.

No baseline differences were noted in age, BMI, anxiety, depression between Veterans and non-Veterans (all $p > .05$)

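### Section 10.1 still states 22 completers per group and 80% power; no power or detectable effect is given for the 24 completers the trial was limited to (about 60% at d = 0.80)

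*Combined protocol and SAP*

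**What the plan says.** Section 10.1 (Sample Size) sets the target at d = 0.80 for emotional well-being and PBMC telomerase activity. The test is specified thus: "Based on a one tailed superiority test of improvement (active > sham CES treatment) and an alpha = .05". The result is that "22 subjects per group are required to provide adequate statistical power (80%) for the analysis", with the supporting output "Noncentrality parameter=2.59, Critical $t(40)=1.68". The section ends with a commitment: "To meet this criteria we will include 22 completed subjects per group". Section 5 also gives 22 completers per group as the aim.

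Section 4.2 (Study Population) opens with the same aim and then records the change: "The study enrollment was limited to 24 completed subjects based on insufficient resources to complete the study beyond the extended recruitment period". Section 13.2 gives the split: "11 subjects completed the Sham treatment and 13 completed the active treatment".

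Section 13.1 says that the study was originally powered for 44 and recruited well short of that. It adds: "The results should be interpreted with caution as the study was likely underpowered". Section 14 says that the small sample makes the telomere-length result hard to interpret.

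**The concern.** Section 4.2 was updated when recruitment stopped, but section 10.1 was not. It still speaks in the future tense of 22 completers per group and has no pointer to the limit. A reader who goes straight to the statistical analysis plan therefore finds only one size and one power figure, and both belong to a trial about twice as large as the one run (44 against 24 completers).

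Section 13.1 warns of low power without a number, although the plan's own inputs are enough to supply one for a simple comparison of completers. Without it, the reader cannot tell whether the loss of sensitivity at the planned effect was slight or substantial.

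**Working it through.** **Inputs.** From section 10.1: d = 0.80 (in SD units), alpha = 0.05 one-tailed, target power 80%, 22 per group, printed noncentrality parameter 2.59 and 40 degrees of freedom. From section 4.2: 24 completers. From section 13.2: 11 sham, 13 active. From section 10.2.1: a one-tailed independent-groups t-test, to be carried out as a contrast in a mixed model.

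**Method.** For a two-sample t-test, the noncentrality parameter is d × √(n₁n₂/(n₁+n₂)) and df = n₁ + n₂ − 2. Power is the probability that a noncentral t variable exceeds the one-tailed 5% critical value.

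**Step 1: the plan's own figure.**
- 22 per group: 0.80 × √(484/44) = 2.65, df 42.
- 21 per group: 0.80 × √(441/42) = 2.59, df 40.

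**Step 2: the achieved size.**
- 11 and 13: 0.80 × √(143/24) = 1.95, df 22.
- 12 and 12 (an even split): 0.80 × √(144/24) = 1.96, df 22.

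| Completers | Noncentrality | df | Critical t | Power |
|---|---|---|---|---|
| 20 + 20 | 2.53 | 38 | 1.686 | 79.9% |
| 21 + 21 | 2.59 | 40 | 1.684 | 81.7% |
| 22 + 22 | 2.65 | 42 | 1.682 | 83.3% |
| 12 + 12 | 1.96 | 22 | 1.717 | 60.0% |
| 11 + 13 | 1.95 | 22 | 1.717 | 59.8% |

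**Reading the table.** The stated sample size reproduces: 21 per group is the smallest size reaching 80%, and 22 is one more. The printed 2.59 and 40 degrees of freedom match 21 per group exactly. They do not belong to 22, where power is 83.3%. A two-sided test does not explain the figures, since it would give 73.6% at 22 per group.

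**Step 3: size of the shortfall.** At the achieved size, power for d = 0.80 is 59.8%. That is 80 − 59.8 = about 20 points below the stated figure, and 83.3 − 59.8 = about 23.5 points below the actual power at 22 per group. A normal approximation for 11 and 13 gives 62%, so the answer does not depend on the method.

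**Step 4: detectable effect.** Solving for 80% power gives d = 1.05 with 11 and 13 completers, against 0.76 with 22 per group.

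**The case against.** The strongest reply is that the shortfall is already disclosed and that section 10.1 simply records the plan. Section 4.2 puts the aim of 22 per group and the limit of 24 in one paragraph, with the reason. Section 13.1 identifies 44 as the original basis for power, calls feasibility a failure and urges caution. Section 10.1 looks forward and section 4.2 looks back, so they can be read as plan and outcome. Most of this stands. The 80% is attached to 22 per group throughout, and a reader who infers that the documents conceal the loss of power, or claim 80% for 24 subjects, has no support in the text. What remains is that section 10.1 has no label or cross-reference, and that no sensitivity figure is given for the achieved size.

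A second reply is that power calculated afterwards adds little, and that once data exist an interval around the estimate shows precision more directly. An interval would be a useful complement. But the 60% is not derived from the observed effect. It uses the pre-specified effect, alpha and sidedness with the achieved numbers, so it is a legitimate update of the planning statement.

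A third reply is that section 10.2 calls for a mixed-model contrast and for intention-to-treat as well as completer analyses of the behavioural measures. This stands and limits the figure. The documents give neither the visit correlation nor the variances needed to compute power for that contrast.

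**Conclusion.** The point holds as an unrevised sample-size section with no sensitivity figure for the achieved size. For a completers-only independent-groups t-test at one-tailed alpha 0.05 with 11 and 13 subjects, power at d = 0.80 is about 60% and the effect detectable with 80% power is about d = 1.05. These figures rest on that test and on the planned d. The slip in the printed noncentrality parameter and degrees of freedom is minor, since it favours the plan: 22 per group would have given slightly more than 80% power.

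Three further inferences are tempting but not supported:

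- **That the telomere-length null is being read against the 80% figure.** Section 10.1 names telomerase activity, which section 13.4.2 says was not analysed. It states no power for telomere length. One subject also lacked enough sample for that measure, and section 14 already warns about the small sample.
- **That any null result at this size tells us nothing.** That depends on the interval around the estimate, not on power alone.
- **That section 14 needs a warning against sizing the next trial from the observed HADS effect.** Section 14 says only that larger studies are needed to confirm the result. It proposes no such sizing.

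**What to change.** 1. In section 10.1, label 22 completers per group as the original target and refer to section 4.2.
2. In section 10.1, add: *Enrolment closed at 24 completers (11 sham, 13 active). For a completers-only independent-groups t-test at one-tailed alpha 0.05, power for d = 0.80 is about 60%, and the smallest effect with 80% power is about d = 1.05; power of the mixed-model or intention-to-treat contrast may differ.*
3. In section 13.1, give the same figures beside the existing remark on low power.
4. In section 10.1, correct the printed parameters: 22 per group corresponds to a noncentrality parameter of 2.65, 42 degrees of freedom and 83.3% power. The printed 2.59 and 40 belong to 21 per group, with 81.7%.

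The change is to wording only, with no new patients, data or analyses. The cost is that the stated power becomes less favourable.
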